#### 7.5.1.6 Week 104 / End of Study

SOBI003 is administered as weekly infusions; a +/- 1-day window is applied. The patients will return to the hospital the day prior to or on the day of the last infusion. AEs and use of concomitant medications during non-hospital stay are captured. The actigraph and accompanying actigraph log are collected.

##### 7.5.1.6.1 Week 104, Day 1 Assessments

Prior to start of the infusion, the following is performed:

- Vital signs are assessed

- General appearance and skin are assessed
- Blood and urine is obtained for safety laboratory
- Blood and urine is obtained for HS assessment
- Blood is obtained for immunogenicity and PK assessments
- When separate consent for future research has been provided, serum samples will also be collected for storage at the central laboratory.

Within 30 to 60 minutes prior to start of each SOBI003 infusion, a single dose of a non-sedative antihistamine is administered. SOBI003 is administered in accordance with Section 7.4.5.

Vital signs are assessed approximately mid-infusion as described in Section 7.5.5.4. As soon as possible following end of infusion, a blood sample is collected for PK evaluation. Vital signs and general appearance and skin are assessed within an hour of completing the infusion.

The parent/caregiver completes the CSHQ questionnaires, preferably during Day 1.

#### 7.5.1.6.2 Week 104, Day 2 to 7 Assessments

General anesthesia is applied in accordance with local routines at the study site. CSF sampling for PK, ADA, and HS assessments and MRI scanning of brain, liver and spleen are completed while the patient is anesthetized. The order of the procedures should preferably be as stated. Should this not be feasible for an individual patient, then effort should be made to have the assessments performed in the same order as they were performed in the FIH study ([SOBI003-001](#)). When separate consent for future research has been provided, CSF will also be collected for storage at the central laboratory.

At the time of CSF sample collection Day 2, a PK blood sample will also be collected. In case the time point for the CSF sample is deviating from the planned time point, the blood samples should be adjusted accordingly.

On Day 3, the VABS-II is assessed by parent/caregiver (refer to Section 7.5.3.2).

The parent/caregiver completes the PedsQL questionnaire, preferably during Day 4.

Based on the patient's developmental age, as determined by the VABS-II score, the BSID-III and/or KABC-II tests are conducted for assessment of neurocognition, language and motor function (see Sections 7.5.3.1, 7.5.3.2, and 7.5.3.6, respectively). If *only* BSID-III or *only* KABC-II is to be assessed, then this should be done on Day 7. If *both* BSID-III and KABC-II should be assessed, then the BSID-III should be administered on Day 4 or 5 and the KABC-II on Day 7.

On Day 7, a neurological and a complete physical examination are performed, an ECG is conducted and height, weight and head circumference are obtained. In addition, blood is collected on Day 8 (approximately 168h after start of SOBI003 infusion) for PK analyses as specified in Section 7.5.5.1.

The patient may be discharged from the hospital 1 hour or later after start of the infusion. The patient will then return to the hospital for study assessments as detailed in Schedule of Events (Table 7).

For patients that are permanently discontinuing SOBI003 treatment, serum samples for PK and ADA analyses should be obtained 30 to 40 days after last SOBI003 infusion. Patients with ADA-positive samples should continue to be followed in accordance with Sections 7.5.4.3 and 7.5.5.1.

#### **7.5.1.7 Weeks of dose adjustments**

During the study there may be situations where individual patients or all study patients will increase or reduce their treatment dose, please refer to 7.4.4 and 7.4.5 for more details. In such situations, a more extensive initial schedule of assessments will follow.

Dose adjustments will be avoided during Weeks 48 to 52 and 100 to 104, in order not to interfere with study efficacy assessments on Week 52 and 104, respectively. Any requested dose adjustment during this time should be postponed until after these assessments have been completed, if not considered medically justified by the investigator.

##### **7.5.1.7.1 First 3 weeks following a SOBI003 dose adjustment**

SOBI003 is administered as weekly infusions; a +/- 1-day window is applied. The patients will return to the hospital the day prior to or on the day of the last infusion. AEs and use of concomitant medications during non-hospital stay are captured.

Prior to start of the infusion, the following is performed:

- Vital signs are assessed
- General appearance and skin are assessed
- Blood and urine is obtained for safety laboratory
- Blood and urine is obtained for HS assessment
- Blood is obtained for immunogenicity (only on week 3) and PK assessments (on weeks 1 and 3)
- A pulse-oximeter is applied

Within 30 to 60 minutes prior to start of each SOBI003 infusion, a single dose of a non-sedative antihistamine is administered. SOBI003 is administered in accordance with Section 7.4.5.

At hourly intervals during the infusion, (i.e. at approximately 1, 2 and 3 hours after start of infusion) vital signs, general appearance and skin are assessed. As soon as possible following end of infusion, a blood sample is collected for PK evaluation (only on week 1). Vital signs and general appearance and skin are assessed within an hour of completing the infusion, and the continuous pulse oximetry is discontinued.

Vital signs, general appearance and skin are assessed within 6-7 hours after start of infusion, and also within 8 to 12 hours after start of infusion, as well as on Day 2 and 3.

On Day 8 (only on week 1) a blood sample for PK evaluation is collected (pre-infusion the following weekly dose).

The patient may be discharged from the hospital 48 hours after start of the infusion. The patient will then return to the hospital for study assessments on Days 3 and 8.

If dose adjustment is a decrease in dose as a result of study dose selection for forthcoming studies, and there are no safety concerns, the patient may be discharged 1 hour or more after the end of each infusion. In such situations the assessments should follow the schedule with the exemption that the vital signs, general appearance and skin assessments within 6-7 hours after start of infusion, and also within 8 to 12 hours after start of infusion, as well as on Day 2 and 3 may be excluded as per investigator decision.

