- Change from baseline at Weeks 52 and 104 in fine motor function AEq score as assessed by the BSID-III motor subtest and the VABS-II

The endpoints relating to the 8th secondary objective are:

- Change from baseline at Weeks 52 and 104 in sleep pattern as assessed by the Children's Sleep Habits Questionnaire (CSHQ) score
- Change from baseline at Weeks 52 and 104 in sleep-related variables as assessed by actigraphy (including total sleep time, total day- and night time sleep duration, sleep latency, sleep efficiency, number of nocturnal awakenings, and wake after sleep onset)

The endpoints relating to the 9th secondary objective are:

- Occurrence of ADAs against SOBI003 in serum at Weeks 38, 52, 78 and 104, and adjacent to dose adjustments (seroconversion rate, time to seroconversion, transient/persistent). For patients with confirmed ADA positive serum samples, the following additional endpoints apply; ADA titers and IgG subclasses in serum, and presence of neutralizing antibodies (NAb) in serum.
- Occurrence of ADAs against SOBI003 in CSF at Weeks 52 and 104 (conversion rate, time to occurrence, transient/persistent). For patients with confirmed ADA positive CSF samples, the following additional endpoints apply: ADA titers and presence of NAb in CSF.

The endpoints relating to the 10th secondary objective are:

- Serum SOBI003 multiple-dose PK parameters at Weeks 38, 52, 78 and 104, and adjacent to dose adjustments;  $t_{\text{End of inf}}$ ,  $C_{\text{End of inf}}$ ,  $C_{\text{Pre-dose}}$ ,  $AUC_{0-168h}$ ,  $CL$
- SOBI003 concentrations in CSF at Weeks 52 and 104.

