**Table 8 Detailed schedule of events – Following a SOBI003 dose adjustment - first 3 weeks**

Week	Following a SOBI003 dose adjustment – First 3 weeks												
	1, 2, 3 (following dose adjustment)												
	Day	1	1	1	1	1	1	1	1	1	2	3	8
Time	Pre-inf	0	1:00	2:00	3:00	4:00	4:01 - 5:00	6:00 – 7:00	8:00 - 12:00	24	48	168 (pre-inf)	
Concomitant therapy	X		X	X	X		X	X	X	X	X	X	
Physical examination (general appearance and skin)	X		X	X	X		X	X	X	X	X		
Vital signs	X		X	X	X		X	X	X	X	X		
Continuous pulse-oximetry	→												
Antihistamine	X												
SOBI003 administration													
Start of infusion		X											
Stop of infusion						X							
Adverse events	X	X	X	X	X	X	X	X	X	X	X	X	
Blood sampling for:													
Safety laboratory	X												
Immunogenicity	X a												
HS	X												
PK	X b					X c, d						X d	
Urine collection for:													
Safety laboratory (Dipstick)	X												
HS	X												

a. Only on week 3

b. Collected on Weeks 1 and 3 following dose adjustment.

c. PK sample should be collected as soon as possible following end of infusion.

d. Collected on Weeks 1 following dose adjustment.

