**Table 13 Safety laboratory assessment time points**

Analyses	Study visit	Sampling time point(s)
Biochemistry (1.5 mL blood): Aspartate aminotransferase (AST), Alanine aminotransferase (ALT), Total bilirubin (if >upper limit of normal [ULN] then also direct and indirect bilirubin), Creatinine, Albumin, Potassium (K), Sodium (Na), Calcium (Ca), non-fasting Glucose, and C-reactive protein (CRP). Hematology (0.5 mL blood): Hemoglobin (Hb), Erythrocytes, White blood cell count (WBC), Differential blood count and Platelet count. Coagulation (1.7 mL): PT/INR, APTT, and Fibrinogen. Urinalysis (dip-stick analyses, central laboratory): pH, Glucose, Proteins, and Blood	Weeks 38, 52, 78 and 104	Pre-infusion (Day 1)
	In case of SOBI003 dose adjustment	For the first 3 infusions following dose adjustment: Pre-infusion (Day 1)
C-reactive protein (hsCRP), IL-1ra, TNF $\alpha$ , IgE, and tryptase (6.4 mL blood)	In case of infusion/anaphylactic reaction	

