#### 7.5.4.3 Immunogenicity

Serum and CSF samples are collected for central laboratory analysis of SOBI003 ADAs by a validated immunoassay method (York Bioanalytical Solutions Limited, York, UK). Assays are being developed for assessment of neutralizing antibodies, both for antibodies inhibiting cellular uptake and for enzyme activity inhibiting antibodies (BioAgilytix, Hamburg, Germany). At each sampling occasion, a blood volume of 1.5 mL will be collected.

Serum samples are collected prior to start of SOBI003 infusion at Weeks 38, 52, 78 and 104, and during Early Termination. Triplicate aliquots are required for each sampling time point.

CSF samples (0.5 mL) are collected at Weeks 52 and 104.

If the dose of SOBI003 is adjusted in a patient, serum samples are collected prior to start of the first adjusted infusion and then prior to the 3rd adjusted infusion i.e., at 2 occasions per dose adjustment.

For patients with an ADA-positive serum sample, the following will also be determined in serum: ADA titer, IgG subclasses, and presence of NAb.

For patients with an ADA-positive CSF sample, the following will also be determined in CSF: ADA titer and presence of NAb.

Should any patient permanently discontinue SOBI003 treatment, then a serum sample will be collected 30 to 40 days after the last SOBI003 administration for ADA assessment. Should the sample be ADA-positive, then the ADA titer will be determined and ADA samplings will continue at approximately monthly basis until the ADA has disappeared or titers have stabilized at a lower level.

The impact of ADAs on the safety, tolerability, and PK of SOBI003 will be explored, as well as the potential impact on HS levels in CSF, serum and urine.

Sampling details are provided separately in the Study laboratory manual.

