In addition, at each time point a sample is collected for immunogenicity, a blood sample is obtained for determination of SOBI003 in serum. In case of a time deviation for the immunogenicity sample, the time for the PK sample should be adjusted accordingly, or an additional PK sample may have to be collected. Therefore, in case the SOBI003 treatment is terminated prior to Week 104, then a PK and immunogenicity sample should be obtained as soon as possible after the decision of early treatment termination, as well as 30 to 40 days after the final SOBI003 infusion.

For patients with confirmed ADA levels, blood samples for PK and immunogenicity analysis should continue in accordance with Section 7.5.4.3.

CSF samples (0.5 mL) are collected during general anesthesia at Day 2 on Weeks 52 and 104 for determination of SOBI003. Triplicate aliquots are required for each sampling time point. At the time of CSF sample collection, a blood sample will also be collected for determination

of SOBI003 in serum. In case the time point for the CSF sample is deviating from the planned time point, the blood samples should be adjusted accordingly.

The exact time of the SOBI003 infusion start and completion as well as of each PK sampling are recorded in the CRF for each patient.

Sampling, storage and shipment details are provided separately in the Study laboratory manual.

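### The antibody sample before the first infusion at a new dose is required in Protocol 7.5.4.3 but left out of the visit schedule (7.5.1.7.1 and Table 8)

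*Protocol*

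**What the plan says.** Protocol 7.5.4.3 (Immunogenicity) states: "If the dose of SOBI003 is adjusted in a patient, serum samples are collected prior to start of the first adjusted infusion". It adds a second sample before the third adjusted infusion and gives the count as "at 2 occasions per dose adjustment".

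Protocol 7.5.1.7.1, which lists the procedures for the first three weeks after an adjustment, states: "Blood is obtained for immunogenicity (only on week 3) and PK assessments (on weeks 1 and 3". Table 8 covers the same weeks. Its footnote on the immunogenicity row reads "a. Only on week 3", and its footnote on the pre-infusion PK row reads "b. Collected on Weeks 1 and 3 following dose adjustment".

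Routine serum ADA samples are taken at Weeks 38, 52, 78 and 104 (Table 2). Table 9, for weeks 4 and 8 after an adjustment, has no ADA sample. Protocol 6.3.1 defines the endpoint as "Occurrence of ADAs against SOBI003 in serum at Weeks 38, 52, 78 and 104, and adjacent to dose adjustments", including seroconversion rate and time to seroconversion.

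**The concern.** One section asks for two ADA samples per adjustment and the operational schedule asks for one. Sites are likely to work from the visit text and Table 8, so the sample at risk is the one before the first adjusted infusion. A missed pre-change sample cannot be recovered later.

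Dose changes are part of the design. Under Protocol 7.1, a Cohort 1 patient may move to the Cohort 2 dose and then the Cohort 3 dose, and the dose finally selected is then applied to everyone. Protocol 7.2 also has the dose adjusted at enrolment.

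Three uses of the data are affected:

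- **Timing and attribution.** If seroconversion or a titer rise is found at the third adjusted infusion, it is less clear when it began and whether it arose on the old or the new dose.
- **Titer by dose.** SAP 16.2 summarises titers by dose. The missing sample would be the final titer on the old dose.
- **Adverse events by titer.** SAP 16.2 classifies each event by the closest preceding titer, and SAP 15.2.1 tabulates events by ADA status when they occur. Events around the first two infusions at the new dose would rest on an older result. The protocol normally requires 48-hour hospital stays for the first three infusions.

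**Working it through.** **1. Count the samples.** Section 7.5.4.3: first + third adjusted infusion = 2. Section 7.5.1.7.1 and Table 8 footnote a: week 3 only = 1. The schedule does not reproduce the stated count of 2.

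**2. Check whether week 1 is the first adjusted infusion.** Table 13 gives the safety laboratory times after an adjustment as "For the first 3 infusions following dose adjustment: Pre-infusion (Day 1", and Table 8 labels the same period weeks 1, 2 and 3. In week 1, Table 8 takes PK before infusion, at end of infusion and at 168 h, which is the set Table 10 lists for the week of the adjustment. Week 1 is therefore the first adjusted infusion and week 3 the third. The sample missing from the schedule is the one before the first.

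**3. Check whether another visit supplies it.** Only a routine ADA visit could, and only when the change falls in that week.

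**4. Age of the last ADA sample at the first adjusted infusion, following Table 8.** Age = week of change − last routine ADA week at or before it. Weeks 48-52 and 100-104 are left out because Protocol 7.5.1.7 avoids changes then.

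| Week of change | Last routine sample | Oldest case |
|---|---|---|
| 38 or 78 | same week | 0 weeks |
| 39-47 | Week 38 | 47 − 38 = 9 weeks |
| 53-77 | Week 52 | 77 − 52 = 25 weeks |
| 79-99 | Week 78 | 99 − 78 = 21 weeks |

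Under 7.5.4.3 the age is always 0. An earlier adjustment at week *a* leaves a week-3 sample at *a* + 2, which shortens the gap:

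- changes at 25 and 30: 30 − 27 = 3 weeks
- changes at 53 and 77: 77 − 55 = 22 weeks
- changes at 79 and 99: 99 − 81 = 18 weeks

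A first change at Weeks 25-37 has no earlier ADA sample in this study. Its gap depends on sampling in the first-in-human study, which these documents do not describe.

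**5. Oldest titer used to classify an adverse event between the first and third adjusted infusions.**

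- Change at 47, event just before the sample at 49: 49 − 38 = 11 weeks.
- Change at 76 or 77, event just before the Week 78 sample: 78 − 52 = 26 weeks.
- Change at 99, event just before the sample at 101: 101 − 78 = 23 weeks.

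Under 7.5.4.3 the titer would be at most 2 weeks old.

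**6. Samples per patient.** With up to three planned changes for a Cohort 1 patient: 3 × 2 = 6 under 7.5.4.3, and 3 × 1 = 3 under Table 8.

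**7. Blood volume at the week 1 pre-infusion draw.** Volumes come from Table 13 and Sections 7.5.4.3, 7.5.5.1 and 7.5.6.1. Biochemistry 1.5 + hematology 0.5 + coagulation 1.7 + heparan sulfate 0.3 + PK 0.3 = 4.3 mL. Adding ADA: 4.3 + 1.5 = 5.8 mL. The planned week 3 draw has the same components including ADA, so it is also 5.8 mL. The single-draw limit in 7.5.1.9 is 8 mL.

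**The case against.** The conflict in the text is not in dispute. The case on the other side is that little follows from it.

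- **Old titers are already accepted.** Routine samples are 78 − 52 = 26 and 104 − 78 = 26 weeks apart, so without an adjustment an event just before Week 78 or 104 is also classified by a titer about 26 weeks old. This stands as context: the worst case is no older than the routine one. But 7.5.4.3 sets a tighter standard at dose changes, and the schedule drops it there.
- **The analysis is thin.** A week 3 sample is still adjacent to the change. SAP 16.2 describes no time-to-seroconversion analysis and no old-dose against new-dose comparison, and it defines induced and boosted ADA against pre-treatment baseline. This stands and limits the severity. Even so, time to seroconversion is part of the endpoint, and the by-dose and by-titer summaries are planned.
- **The commonest change may be covered.** A change at enrolment directly follows the first-in-human study, which may have taken an ADA sample at its last visit. That cannot be settled here.
- **One sample may have been intended.** Section 7.5.5.1 describes only the PK sample before the third adjusted dose as an ADA reference. This is not decisive, because PK before the first adjusted dose is scheduled in any case. The documents do not say which version is meant, but the explicit count of two favours two samples. If one was intended, 7.5.4.3 is wrong and needs correcting.
- **Sites might still follow 7.5.4.3.** It is a protocol requirement, and the laboratory manual is not available here. This makes the loss likely rather than certain.

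**Conclusion.** The inconsistency is real, and no reading reconciles the two instructions. It should be fixed, but it does not threaten the main conclusions. A site following the schedule takes one ADA sample per adjustment instead of two and loses the pre-change one. The last earlier result can then be up to 9, 25 or 21 weeks old, depending on the window.

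These figures are upper bounds that assume no earlier adjustment. No average is given, because the documents do not say how likely a change is in any week. The effect is confined to descriptive immunogenicity and event-by-antibody summaries in 9-12 patients. Earlier samples still show prior ADA status. Overall adverse event counts, sample size, power and the tested hierarchy do not change.

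**What to change.** Change the immunogenicity instruction in Protocol 7.5.1.7.1 and footnote a of Table 8 to Weeks 1 and 3, matching 7.5.4.3 and the pre-infusion PK draws. Apply this to a change at Week 25 as well, unless an ADA sample at Week 24 of the first-in-human study is confirmed as the pre-change sample.

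No extra PK sample is needed. Section 7.5.5.1 states that "at each time point a sample is collected for immunogenicity, a blood sample is obtained for determination of SOBI003 in serum", and that PK sample is already scheduled at week 1.

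The cost is one 1.5 mL tube per adjustment at an existing draw. The 1% single-draw limit in 7.5.1.9 is no more demanding at week 1 than at week 3, since both draws would be 5.8 mL. The four-week total rises by 1.5 mL, so the 3% limit should be checked for the smallest children. ADA is first in that section's priority list if volume is restricted.

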#### 7.5.1.7.2 On Weeks 4 and 8 following a SOBI003 dose adjustment

SOBI003 is administered as weekly infusions; a +/- 1-day window is applied. The patients will return to the hospital the day prior to or on the day of the last infusion. AEs and use of concomitant medications during non-hospital stay are captured.

Prior to start of the infusion, the following is performed:

- Vital signs are assessed
- General appearance and skin are assessed
- Blood is obtained for PK assessments

Within 30 to 60 minutes prior to start of each SOBI003 infusion, a single dose of a non-sedative antihistamine is administered. SOBI003 is administered in accordance with Section 7.4.5.

Vital signs are assessed approximately mid-infusion as described in Section 7.5.4.4. As soon as possible following end of infusion, a blood sample is collected for PK evaluation. Vital signs and general appearance and skin are assessed within an hour of completing the infusion.

On Day 8 a blood sample for PK evaluation is collected (pre-infusion the following weekly dose).

The patient may be discharged from the hospital 1 hour or more after the end of each infusion.

#### 7.5.1.8 Early withdrawal from treatment/study

If the patient is withdrawn from study treatment, the patient should be examined as soon as possible after making the withdrawal decision. AEs and use of concomitant medications are captured. Blood is collected for safety laboratory, HS, immunogenicity and PK assessments. Urine is collected for safety laboratory and HS assessments.

Vital signs are assessed, and a neurological and a physical examination are performed. An ECG is conducted, and height, weight and head circumference are obtained.

The VABS-II is assessed by parent/caregiver (refer to Section 7.5.3.2). The parent/caregiver completes the PedsQL questionnaire.

Based on the patient's developmental age, as determined by the VABS-II score, the BSID-III and/or KABC-II tests are conducted for assessment of neurocognition, language and motor function (see Sections 7.5.3.1, 7.5.3.2, and 7.5.3.6, respectively). If *both* BSID-III and KABC-II should be assessed, then the BSID-III should be administered 2 days prior to the completion of KABC-II.

When possible, study assessments (excluding SOBI003 infusion) of Weeks 38, 52, 78 and 104 should continue in accordance with the Schedule of Events. At minimum, the Early

Termination assessments should be repeated 30 to 40 days after the last SOBI003 administration. Patients with ADA-positive samples should continue to be followed in accordance with Sections 7.5.4.3 and 7.5.5.1.

